Previvors Recharge: A Resilience Program for Cancer Previvors (PreCharge)

NCT06378749

Unique Protocol ID: R43CA275673

March 21, 2023

Unique Protocol

Objective:

The purpose of this research was to assess in a 30-day pilot test the acceptability and feasibility of PreCharge, a digital program delivered via text messaging and online activities designed to increase resilience and adaptive coping among previvors—individuals with Hereditary Cancer Syndromes (HCS) who have not been diagnosed with cancer. PreCharge is tailored to users' levels of resilience and adaptive coping and addresses previvor-specific needs related to: 1) information; 2) healthcare navigation; 3) processing difficult emotions; 4) social support; and 5) self-care.

Design:

As this was a Phase I study, it entailed a single-group, pre-post pilot of the PreCharge program.

The PreCharge program has various components including:

- **Immediate.and.Ongoing.Tailored.Communications;** Following the baseline assessment, participants received onscreen feedback tailored to their responses. This feedback highlighted the importance of resilience and adaptive coping for previvors and described how the program aimed to enhance those skills. Participants' responses also guided daily text communications. Daily text messages provided tailored guidance—matched to each user's responses—about resilience and coping strategies. Periodic reassessments conducted via SMS ensured that communications remained relevant to participants' evolving needs.
- **Online.Portal.** Upon completion of the baseline assessment, participants gained access to a portal homepage which featured interactive activities and tools designed to address their resilience and coping. The portal included links to additional resources, an account page, and a log-out button. For research purposes, study information was also accessible from this page during the pilot.
- **Just-in_Time.Assistance.** In addition to daily text messages, participants could access “just-in-time assistance” by indicating upcoming medical appointments or texting trigger words. Appointment-related communications were sent via SMS three days before, on the day of, and three days after an appointment to address “scanxiety” and other concerns in a timely manner. Participants could also text trigger words at any time to receive immediate support. In response to trigger words,

PreCharge provided participants with timely guidance for improving moods, practicing gratitude, and managing stress.

Methods:

Recruitment for the 30-day pilot test began in April 2024. Participants were recruited with the help of two leading previvor advocacy organizations: Facing Our Risk of Cancer Empowered (FORCE) and AliveandKick'n. From recruitment materials distributed by our recruitment partners, prospective participants were directed to a study landing page which began with a brief overview of the study, followed by "Frequently Asked Questions," that addressed several elements of informed consent. The landing page also included instructions on how to initiate the brief (about 5 minutes) secure screening assessment.

The study eligibility criteria assessed in the secure screening assessment were:

- Able to read and speak English
- Age 18 or older
- Currently living in the U.S.
- Regular use of a smartphone, the internet, or both
- Regular use of text messaging, email, or both
- Identify as having a Hereditary Cancer Syndrome (HCS)
- Have never been diagnosed with cancer
- Have a "low" level of resilience as indicated by a score of 26 or below on the Connor Davidson Resilience Scale (CD-RISC 10)

The screener excluded individuals who did not meet the study eligibility criteria. Individuals who screened out or who did not consent to study participation were thanked for their time and provided with a list of national resources for previvors.

Eligible participants were invited to provide informed consent. Those who provided informed consent completed a baseline research assessment that assessed confidence to cope, psychological flexibility, depression, and anxiety. After completing the baseline assessment, participants completed their first session, which asked them a series of questions to determine their level of resilience. Based on responses during this first session, the system delivered tailored feedback and queued 30 days worth of daily, tailored text messages focused on resilience. Completing this first session marked the end of the baseline session (baseline research assessment + first session) and granted participants access to their online portal, which featured interactive activities and tools designed to address their resilience and coping. Participants were told they could access their online portal at any time during the 30-day pilot period. As a thank you for completing the baseline assessment, participants received a \$50 gift card.

Four days after completing the first session (which followed the baseline assessment), participants were prompted to complete a brief second session via text message. This session asked participants a series of questions related to an adaptive coping strategy: acceptance. Based on responses during that session, the system delivered tailored feedback and queued daily, tailored text messages about acceptance.

This pattern continued for the remainder of the 30-day pilot period: every four days, participants were prompted to complete a new session via text message, during which they would be asked a series of questions related to either resilience or an adaptive coping strategy; based on their responses, the system delivered tailored feedback and queued daily, tailored text messages related to the construct assessed.

Over the course of the 30-day pilot period, participants could complete up to seven sessions via SMS. The constructs assessed during each session were as follows: 1) resilience; 2) adaptive coping strategy: acceptance; 3) resilience; 4) adaptive coping strategy: active coping; 5) resilience; 6) adaptive coping strategy: venting; 7) resilience.

All daily text messages provided tailored guidance matched to each participant's responses to questions about their resilience and use of adaptive coping strategies, and encouraged users to engage with online portal activities and tools.

Participants received an email 31 days after completing the baseline session (baseline research assessment + first session), participants received an email inviting them to complete the follow-up assessment. Up to four text and five email reminders to complete the follow-up assessment were sent. Non-respondents received up to two telephone calls from the Research Manager to remind them to complete the follow-up assessment and offer them the opportunity to complete the assessment by phone. As a thank you for completing the follow-up assessment, participants received a \$70 gift card.

Pilot participants were 138 previvors. Of the 138 initial participants, 134 completed the follow-up assessment at the end of the 30-day pilot period, resulting in a final sample of 134 previvors.

Simple descriptive statistics were calculated to describe the study sample and to evaluate program utilization and acceptability. Paired t-tests of pre-post differences on several key outcomes, including the primary outcome (resilience as measured by the CD-RISC 10), were conducted.

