### Statistical Analysis Plan

This study involved a single-group, pre-post design. Paired t-tests were used to determine the effect of the *PreCharge* intervention on the primary and secondary outcomes. The primary outcome was change, from pretest (baseline) to posttest (30 day follow-up), in resilience as measured by the Connor Davidson Resilience Scale (CDRISC-10). Secondary outcome measures include change in psychological flexibility (as measured by the Acceptance and Action Questionnaire – version 2 (AAQII). between pretest (baseline) and posttest (30 day follow-up) assessments. Cohen's d was used to assess the magnitude of the differences.

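### Does a pilot whose purpose is acceptability and feasibility need a fuller analysis of them than the SAP gives?

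*Protocol*

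**What the plan says.** The Objective section of the protocol gives one purpose, to "assess in a 30-day pilot test the acceptability and feasibility of PreCharge". The Design section describes a single-group Phase I pilot, and the SAP agrees: "This study involved a single-group, pre-post design".

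The SAP section headed Statistical Analysis Plan sets paired t-tests and Cohen's d. It states that "The primary outcome was change, from pretest (baseline) to posttest (30 day follow-up), in resilience", and the one secondary outcome it names is AAQ-II change, introduced by the word include. It does not mention acceptability, feasibility, use or retention.

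The end of the protocol's Methods section does cover part of this: "Simple descriptive statistics were calculated to describe the study sample and to evaluate program utilization and acceptability". Just before that it reports that "Of the 138 initial participants, 134 completed the follow-up assessment at the end of the 30-day pilot period", and it takes these completers as its final sample. It also describes the effort behind follow-up: "Up to four text and five email reminders to complete the follow-up assessment were sent", then up to two telephone calls to non-respondents, with a $70 gift card on completion. On exposure, Methods says that "participants could complete up to seven sessions via SMS" and counts the first of them as part of the baseline session.

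**The concern.** Set side by side, the purpose and the SAP do not match. The formal inference is about resilience, while the stated question rests on one sentence of unspecified descriptives and neither document defines a feasibility measure. Three misreadings could follow.

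- Use might be described only in people who stayed to follow-up, because the sentence on descriptives comes straight after the one defining a final sample of 134.
- A count of sessions out of seven would credit the first session, which everyone entering the pilot completes as part of enrolment, as engagement with the programme.
- Retention of 97%, achieved with repeated reminders and a payment, might be read as evidence that the programme was used.

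If any of these occurred, the pilot could report feasibility more favourably than its data support.

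**Working it through.** The documents state no sample size calculation, feasibility threshold or target use rate, so there is no design figure to reproduce. The check is how far each possible misreading could move a result.

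**Inputs.** From the protocol's Methods: 138 started, 134 completed follow-up, so 4 did not; up to seven sessions, of which one falls in the baseline session and six are prompted later; up to 4 texts, 5 emails and 2 calls. The values of k, j and s below are assumptions, because the documents report no use data.

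**Retention.** 134/138 = 97.1%. The exact (Clopper-Pearson) 95% interval is 92.7% to 99.2%. The maximum number of reminder contacts is 4 + 5 + 2 = 11. This figure describes study follow-up. The protocol names utilization separately and nowhere offers retention as a measure of use.

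**Denominator.** Let k of the 134 completers and j of the 4 non-completers be users. Describing use in completers differs from describing it in everyone by k/134 − (k + j)/138.

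| k | j | Among 134 | Among 138 | Difference (points) |
|---|---|---|---|---|
| 134 | 0 | 100.0% | 97.1% | 2.9 (largest overstatement) |
| 67 | 0 | 50.0% | 48.6% | 1.4 |
| 67 | 2 | 50.0% | 50.0% | 0 |

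For comparison, the largest exact 95% half-width for any proportion is 8.6 points at n = 138 and 8.75 points at n = 134. Even the extreme case is about a third of that (2.9/8.6 = 0.34).

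**First session.** Suppose use were summarised as sessions completed out of seven, everyone completed the first, and s is the mean number of the six prompted sessions completed. The seven-session share exceeds the prompted-session share by

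(1 + s)/7 − s/6 = (6 − s)/42.

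This is 14.3 points at s = 0, 7.1 at s = 3 (57.1% against 50.0%), 2.4 at s = 5 and 0 at s = 6. The large value needs nobody to complete any later session, a result that a session-by-session table would show at once. The Methods text gives seven as the most a participant could complete. It does not define a use metric.

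**Reading the two documents together.** Resilience is called the primary outcome in both the SAP and the protocol's Methods, so they agree on that. Use and acceptability have a stated, if thin, descriptive analysis in the protocol, and the SAP need not repeat it. Feasibility alone has neither a named measure nor a criterion; retention appears as counts.

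**The case for a change.** The strongest case for a change is that a pilot should specify the analysis of its own purpose at least as carefully as that of a secondary question. The exposures that could be described are identifiable (prompted sessions, portal visits, trigger words, appointment entries), yet none is named as a measure. A short SAP addition would set the denominators, separate the first session from the prompted ones, add exact intervals and label retention as study follow-up, with no new data collection.

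Part of this stands. Feasibility is undefined, and a reader cannot tell from the documents which use and acceptability measures were taken or on whom. A report of the pilot would be clearer for stating them: use on all 138, acceptability on the 134 who answered, the first session shown apart from the rest, and CD-RISC 10 change described as uncontrolled.

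It does not show a fault in the plan. No passage says that use was computed in the 134, that sessions were scored out of seven, or that retention stands for use. Each supposed bias is measured against an analysis the documents do not describe. The exact intervals follow from counts and can be computed by anyone who has them, and the uncontrolled nature of the comparison is already plain from the single-group design. Both documents report the analyses in the past tense, so a feasibility criterion added now would be set after data collection and could not serve as a pre-specified test.

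**Conclusion.** No change to the plan follows. The mismatch between the Objective and the visible SAP text is real, but it is a gap in detail that a competent analyst fills by following the protocol's own sentence on descriptive statistics. The denominator effect is at most 2.9 points, 1.4 if half the completers and no non-completer used the programme, and 0 if use was equal in the two groups. The first-session effect ranges from 0 to 14.3 points and arises only under an assumed summary out of seven. Retention of 97.1% (92.7 to 99.2) is sound as a measure of study follow-up.

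Two limits apply. Part of the SAP was not in the copy reviewed, so absence can be asserted only for the section available, and the list of secondary outcomes is worded as open. The conclusion also assumes that the use records and acceptability items implied by the protocol's Methods exist. If they do not, the report should say that this part of the objective was not assessed.

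### Does admitting email users who do not regularly text undermine a program delivered mainly by text message?

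*Protocol*

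**What the plan says.** The eligibility list in Protocol Methods has two lines on technology. One asks for "Regular use of text messaging, email, or both" and the other for "Regular use of a smartphone, the internet, or both". No other listed criterion mentions texting.

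The Objective calls PreCharge "a digital program delivered via text messaging and online activities". Under Design, "Periodic reassessments conducted via SMS ensured that communications remained relevant"; "Appointment-related communications were sent via SMS three days before, on the day of, and three days after an appointment"; and "Participants could also text trigger words at any time to receive immediate support". In Methods, after the first session the system "queued 30 days worth of daily, tailored text messages focused on resilience", and from then on "every four days, participants were prompted to complete a new session via text message".

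Apart from the eligibility line, email appears only near the end of Methods, for the follow-up invitation and for reminders. Those reminders also went by text, and non-respondents could be telephoned.

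Methods says that utilization and acceptability are summarised with simple descriptive statistics. The SAP specifies paired t-tests and Cohen's d for pre-post change and does not mention the delivery channel.

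**The concern.** Both technology lines are alternatives. Someone who uses the internet and email but seldom texts satisfies each of them and is eligible for a program that reaches participants largely by text.

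The study's stated purpose is acceptability and feasibility, and there is no comparison group. If such people were enrolled and used little of the program, low utilization could mean that the content did not engage them or that they rarely use the channel. Those explanations point to different revisions of the program, and a single whole-sample summary would not separate them. The portal is only a partial answer, because the daily texts were also meant to steer people towards it.

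**Working it through.** The plan states no figure to reproduce. The check sets the eligibility wording beside each description of delivery.

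**Is the gap real?** Yes. A criterion of the form A, B or both is met by B alone. Email alone meets the messaging line, internet use alone meets the device line, and nothing else requires texting.

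**What depends on text?** Daily messages, reassessments, appointment messages and trigger words are by text. Sessions 2 to 7 are at least prompted by text. Methods also refers to up to seven sessions by SMS, although it places the first session within the baseline session. It does not settle whether a later session was completed by text or only announced that way.

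**What does not depend on text?** The onscreen feedback after baseline and access to the portal. The follow-up assessment, which supplies the primary outcome, was opened by an email invitation and supported by text, email and telephone reminders. An infrequent texter is therefore not lost to the primary analysis because of the channel.

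**Does the criterion conflict with delivery?** Only if a person who does not regularly text also cannot receive or answer texts. The documents do not say so. Methods describes messages queued and prompts sent with no exception noted, and text reminders for follow-up. Whether a text-capable phone was checked at enrolment is not stated either way.

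**Can the effect be sized?** No. It needs k, the number of the 138 participants who did not regularly text, and k is not given. Under the extreme assumption that these people used no text content at all, the highest possible share completing any of sessions 2 to 7 is (138 − k)/138:

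- k = 0: 138/138 = 100%
- k = 1: 137/138 = 99.3%
- k = 7: 131/138 = 94.9%
- k = 14: 124/138 = 89.9%

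A fall of 5 percentage points needs at least 7 such people (6/138 = 4.3%, 7/138 = 5.1%). A fall of 10 points needs at least 14 (13/138 = 9.4%, 14/138 = 10.1%). This only converts an assumed count into a percentage and would hold for any hypothetical group of non-users. It is not evidence that utilization was affected, and answering even some messages would make the loss smaller.

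**Does the primary analysis suffer?** The paired t-test uses each participant's own difference. An infrequent texter contributes a valid difference, and the mean describes change among those analysed, whatever their exposure to the program.

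**The case for a change.** The strongest case for acting is that the gap follows from the text whatever k turns out to be. Closing it would cost one eligibility line and a split screener item, or one descriptive table or limitation sentence for the completed pilot. Since feasibility is the purpose, separating low engagement from low channel use would also help in interpreting the results.

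Part of this stands. The wording is loose, and a breakdown by baseline texting habit would help explain the utilization figures if the screener captured texting separately from email.

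It does not follow that whole-sample utilization is unreadable without that breakdown. Utilization always pools people with different habits, and here it describes the population the criteria define. Requiring regular texting would also exclude people who can receive texts but seldom send them, and would limit the results to habitual texters. Confirming a text-capable phone would secure delivery with less narrowing. Splitting pre-post change by texting status would add little: the group may be empty or very small, and no effect on that analysis has been shown.

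**Conclusion.** No change to the plan is called for. The eligibility line is broader than the delivery channel, but admitting infrequent texters is a defensible choice for a Phase I feasibility pilot, and narrowing entry would exchange breadth for a more uniform sample. The pilot is complete, so its eligibility cannot be altered. What remains is a wording point for any reuse of the protocol (whether being able to receive and send texts was required, or whether an email route existed) and, if the screener recorded it, a simple count of infrequent texters with a description of their utilization. Analysts can supply that without amending anything.

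The size of any effect on utilization is unknown and may be zero. This conclusion rests on reading regular use as habit and not access, and on taking at face value the description of texts going to participants without exception. It would need another look if records showed that an appreciable number of the 138 could not receive texts at all.

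### Is programme utilisation left without a usable denominator, in people or in sessions?

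*Protocol*

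**What the plan says.** The protocol's Objective is explicit: "The purpose of this research was to assess in a 30-day pilot test the acceptability and feasibility of PreCharge". In Methods, the account of the sample gives 138 participants at the start, of whom "134 completed the follow-up assessment at the end of the 30-day pilot period, resulting in a final sample of 134 previvors". The closing paragraph of Methods adds: "Simple descriptive statistics were calculated to describe the study sample and to evaluate program utilization and acceptability". It names no utilisation metric and no analysis set. The SAP text available covers paired t-tests and Cohen's d for the resilience and psychological flexibility outcomes, and does not deal with utilisation.

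On sessions, Methods places the first one at enrolment: "Completing this first session marked the end of the baseline session". It continues: "Four days after completing the first session (which followed the baseline assessment), participants were prompted to complete a brief second session via text message". For the rest of the period, "every four days, participants were prompted to complete a new session via text message". The total is stated once: "participants could complete up to seven sessions via SMS". The list of contents follows: "The constructs assessed during each session were as follows: 1) resilience; 2) adaptive coping strategy: acceptance; 3) resilience", and so on up to a seventh entry, which is again resilience.

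**The concern.** Two denominators seem unsettled.

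- **People.** The 134 are defined by answering the follow-up survey. Use of a programme during 30 days need not depend on answering a survey afterwards. If utilisation was tabulated on the 134, it was tabulated on a group selected for responsiveness.
- **Sessions.** If the first session belongs to the baseline visit, only six of the seven listed sessions are described as following a text prompt, yet seven are attributed to SMS. A prompt every four days for 30 days would also give seven prompts, which makes eight sessions with the first.

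If utilisation was reported as sessions completed out of seven, the baseline session would count as programme use, and someone who ignored every prompt would still show some. In a pilot meant to judge feasibility, that would cloud a main descriptive finding.

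**Working it through.** **Inputs.** From the protocol's Methods: 138 participants, 134 follow-up completers, a 30-day period, a four-day interval, seven listed sessions, and the first session completed at baseline (taken as day 0).

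**1. People.**
- The stated count reproduces: 138 − 4 = 134. Retention is 134/138 = 97.1% and loss is 4/138 = 2.9%.
- Suppose *x* of the 134 used the programme. On all 138 the rate lies between *x*/138 (none of the four used it) and (*x* + 4)/138 (all four did).
- The largest fall is at *x* = 134: 134/134 − 134/138 = 2.9 points. The largest rise is at *x* = 0: 4/138 = 2.9 points.

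The documents give no utilisation rate, so the rates below are assumed:

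| Assumed rate in 134 | Range on 138 |
|---|---|
| 67/134 = 50.0% | 67/138 = 48.6% to 71/138 = 51.4% |
| 107/134 = 79.9% | 107/138 = 77.5% to 111/138 = 80.4% |
| 127/134 = 94.8% | 127/138 = 92.0% to 131/138 = 94.9% |

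**2. Sessions, statements side by side.**
- *Narrative and list.* The first session is resilience, at baseline. The second is acceptance, prompted four days later. The list opens in the same order. Sessions 1 to 7 therefore fall on days 0, 4, 8, 12, 16, 20 and 24: seven in all, six of them prompted by text.
- *Interval run to the end of the period.* Prompts fall on days 4, 8, 12, 16, 20, 24 and 28: seven prompts, or eight sessions with the first. The day-28 prompt has no entry in the list.
- *Stated total.* At most seven. Taken as a cap on the four-day pattern, this agrees with the list and implies no eighth session. The reference to SMS then fits the first session awkwardly, though the protocol never states outright how that session was delivered.

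**3. What the session count could do, if utilisation were a share of sessions (assumed).**
- With *k* of six prompts answered, the prompted share is *k*/6. Counting the baseline session gives (*k* + 1)/7.
- The difference (*k* + 1)/7 − *k*/6 is 14.3 points at *k* = 0, 7.1 points at *k* = 3 (57.1% against 50.0%) and 0 at *k* = 6.
- If seven prompts were offered, three answered is 3/7 = 42.9%.

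**4. Resilience.** Assume a standardised change of 0.50 in the 134 (SD of change 1) and zero change in the other four. The mean becomes 0.50 × 134/138 = 0.4855, the SD becomes 0.989, and d = 0.4855/0.989 = 0.49.

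**The case for a change.** The strongest case for acting is that utilisation bears directly on the stated purpose, yet nothing says how it is calculated, and neither simple reading of the session text is clean. If the seven are the prompts on days 4 to 28, the list should not open with the baseline session. If the seven include the baseline session, the reference to SMS is wrong for one of them and the literal interval leaves a prompt over. The second session was timed from completion of the first. If later prompts were timed the same way, the number offered would differ between participants: with assumed delays of 1, 2 or 4 days per session, six, five or four prompts would fit in 30 days.

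Part of this stands. The wording on SMS and the four-day interval does not sit squarely with the list, and a stated metric and N would help a reader.

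The rest is weaker. The protocol gives one explicit count; the competing ones are inferred. The delays are invented, and the text describes a regular four-day pattern. The session percentages need a metric that the documents never name. The Design section describes a portal, daily texts, appointment messages and trigger words, and use of these could be summarised without any session denominator. That utilisation was restricted to the 134 is also an inference. Calling completers the final sample is natural where the main tests need paired scores, and the protocol does not say that the other four were left out of the usage summaries.

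**Conclusion.** No change to the plan follows. The person denominator is a reporting gap that an analyst fills by stating the N. Both candidates are disclosed, the choice is worth at most 2.9 points, and its sign depends on four people about whose use the documents say nothing. A feasibility conclusion would be sound on either N.

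The session text contains a clerical looseness: one of the seven sessions attributed to SMS was completed at baseline, and a literal four-day pattern gives a day-28 prompt that is not listed. Those passages should be reconciled with each other when the study is written up; this review does not say which schedule was delivered. No stated analysis rule is shown to give a wrong answer. The shift of up to 14.3 points rests wholly on the assumption that utilisation is a share of sessions with the baseline session counted, and it shrinks to nothing for participants who answered all six prompts.

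The paired tests do not use the session count. On the assumption of no change in the four non-completers, an assumed effect of 0.50 would become about 0.49, so an added all-138 resilience analysis would bring little.
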